8.2.2 Non-Hematologic Toxicity

Patients who experience a Grade 3 or 4 non-hematologic AE deemed related to bomedemstat (possibly, probably or definitely) may have their dose adjusted downward by 50% if the PI deems it safe for the patient to continue on bomedemstat. Any patient that experiences an AE that results in discontinuation of bomedemstat therapy may begin alternative cytoreductive therapy to lower platelets and hematocrit within 24-48 hours.

8.2.3 Stopping Rules

Bomedemstat will be discontinued in the event of any one of the following:

- Post Grade 3 or 4 non-hematologic AE deemed related to bomedemstat (possibly, probably or definitely), the patient's clinical condition either worsens at any time or fails to demonstrate significant improvement within 14 days, or the PI deems it unsafe for the patient to continue on bomedemstat.
- Post temporary interruption of bomedemstat due to platelet counts $<50 \times 10^9/L$ (50 k/ μL), the patient's platelet counts do not return to $>150 \times 10^9/L$ (150 k/ μL) within 21 days.

Patients who discontinue bomedemstat will enter follow-up beginning with the EoT visit.

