All patients will begin dosing on Day 1 at the starting dose of 40 mg/d and be treated daily for 52 weeks. Through the use of dose titration, the dose of bomedemstat will be adjusted for each patient to that dose that provides sufficient exposure to safely inhibit the activity of LSD1 in hematopoietic cells for a fraction of the dosing cycle without resulting in Grade ≥ 1 thrombocytopenia. Given the short lifespan of a human platelet compared to a red cell, approximately 7 days *versus* approximately 120 days, patients will be dosed using the platelet count as a biomarker of the activity of bomedemstat on the inhibition of LSD1. Details on the selection and rationale for the starting dose and titration schedule can be found in Section 3.7. Dose-titration, both upward and downward, is contingent on a hematology assessment. The first up-titration is not permitted before Week 6, and the second up-titration may occur no sooner than 6 weeks after the first up-titration (*e.g.*, if an up-titration occurs at Week 6, the next up-titration may not occur until Week 12). Beginning at Week 16, up-titrations are permitted no more frequently than every 4 weeks from the previous up- or down-titration. Down-titrations can be made (or the current dose maintained) at any time in the best interest of the patient. Up-titrations will be made in increments of 5 or 10 mg/d, and down-titrations in decrements of 10 mg/day.

The hematocrit titration target expected to be associated with a clinically significant therapeutic effect is:

- A hematocrit <42%

Titration and re-challenge rules to be used for titration assessment purposes, based on evaluation of platelet, ANC and hematocrit (Hct) counts are noted below.

Table 1: Titration and Re-challenge Rules

Bomedemstat Titration and Re-challenge Rules				
Important: ANC $\geq 0.5 \times 10^9/L$ (500 neutrophils/ μL) is needed for up-titration. For ANC below this threshold, maintain or adjust the current dose in accordance with the rules below.				
Hematology Assessment		Titration and Re-challenge Rules		
Plt Count ($\times 10^9/L$)	Hct %	Titration?	Titration Rule	Re-challenge Rule [¥]
≥ 450	N/A	Up-titrate [¤]	Increase by 10 mg/d [¤]	N/A
150 – <450	42% – 45%	Up-titrate [¤]	Increase by 5 mg/d [¤]	N/A
150 – <450	<42%	Maintain dose	N/A	N/A
50 – <150	N/A	Down-titrate	Decrease by 10 mg/d	N/A
<50	N/A	HOLD DOSE	N/A	At 50% of prior dose** when platelets return to ≥ 100

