ANC, absolute neutrophil count; CBC, complete blood count; Hct, hematocrit; N/A, not applicable; Plt, platelet. [¤] The first up-titration is not permitted before Week 6, and the second up-titration may occur no sooner than 6 weeks after the first up-titration (e.g., if an up-titration occurs at Week 6, the next up-titration may not occur until Week 12). Beginning at Week 16, up-titrations are permitted no more frequently than every 4 weeks from the previous up- or down-titration. Down-titrations can be made (or the current dose maintained) at any time in the best interest of the patient. ^{**} Patients requiring a dose hold should have CBC with differential monitored at least weekly for safety and to enable re-challenge as soon as platelet counts return to $\geq 100 \times 10^9/L$, if safe to do so. Re-challenge at 50% of the previous mg/d dose. [¥] Upon re-challenge, all of the above rules reapply.				

If needed, please consult the Medical Monitor regarding dose modifications of bomedemstat should an AE requiring a dose reduction occur and for the management of clinically significant changes in platelets, neutrophil counts, or other hematologic parameters.

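### After a hold for low platelets, the re-challenge, down-titration and stopping rules use unlinked thresholds and an undefined 21-day clock, and at Day 21 they can give opposite instructions on one count

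*Combined protocol and SAP*

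**What the plan says.** All platelet counts here are × 10⁹/L.

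- **Hold and re-challenge (Section 7.2.2, Table 1; repeated in the synopsis).** Dosing is held below 50. Re-challenge is "At 50% of prior dose when platelets return to" at least 100. The footnote requires at least weekly blood counts during a hold, "to enable re-challenge as soon as platelet counts return to" that level, if this is safe.
- **After re-challenge (Table 1 footnote).** "Upon re-challenge, all of the above rules reapply". The row for platelets of 50 to <150, at any hematocrit, reads "Decrease by 10 mg/d". Another footnote gives latitude: "Down-titrations can be made (or the current dose maintained) at any time in the best interest of the patient".
- **Stopping (Section 8.2.3; repeated in the synopsis).** "Bomedemstat will be discontinued in the event of any one of the following". The platelet item begins "Post temporary interruption of bomedemstat due to platelet counts" below 50 and applies where "platelet counts do not return to" more than 150 within 21 days.
- **Interruption of dosing (Section 7.2.2.3).** Re-challenge follows once platelets are back at a required level, for which no number is given.

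**The concern.** Two platelet values, 100 and 150, govern recovery from the same event, and no section relates them. One rule puts the patient back on a platelet-lowering drug at 100. The other takes the patient off it permanently unless the count passes 150 by a deadline with no stated start. Between the two values, the reapplied titration row also calls for a lower dose.

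Section 3.6 names severe thrombocytopenia as the greatest clinical risk in this trial. Safety and tolerability is a primary objective (Section 4.1), and Section 12.5 tabulates discontinuations due to treatment-emergent adverse events. Sections 6.3, 6.6, 8.1 and 11 all refer to the stopping rules, and under Section 8.1 meeting one may prompt an expedited SAB review. With about 15 sites and about 20 patients, two sites could handle the same platelet course differently. The discontinuation count would then partly reflect how the text was read.

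**Working it through.** The plan states no figure to reproduce. The check is to apply the rules as written to the same count.

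**Inputs:** hold below 50; restart at ≥100 at 50% of prior dose; decrease of 10 mg/d at 50 to <150; maintain at 150 to <450 with hematocrit <42%, or increase by 5 mg/d with hematocrit 42% to 45%, within the timing limits on up-titration (all Table 1). Discontinue if not >150 within 21 days (Section 8.2.3).

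**Reading A: the clock starts with the hold, and no count has yet exceeded 150.**

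| Platelets | Re-challenge rule | Titration row | Stopping rule at Day 21 |
|---|---|---|---|
| 50 to 99 | not yet allowed | decrease 10 mg/d, though no dose is being given during a hold | discontinue |
| 100 to <150 | restart at 50% | decrease 10 mg/d | discontinue |
| exactly 150 | restart at 50% | maintain or increase | discontinue |
| above 150, below 450 | restart at 50% | maintain or increase | not met |

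- Before Day 21 the last column does not apply. At 100 to <150 only the restart and decrease rules meet.
- At Day 21, a patient first reaching 100 to 150 satisfies the re-challenge rule and the mandatory stopping rule on one count.
- A patient restarted earlier who has stayed at 100 to <150 is to be discontinued at Day 21, while Table 1 would continue treatment at a lower or maintained dose.

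**Reading B: the clock starts at re-challenge.** The clash between restarting and stopping on one count disappears. A restarted patient still at 100 to <150 after 21 days nevertheless falls in both the decrease row and the stopping rule. A patient who never reaches 100 never starts the clock.

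**Rise needed after restart.** Required rise = 150 / count at restart − 1. From 100: 150/100 − 1 = 50%. From 120: 150/120 − 1 = 25%. Each must be exceeded, because the test is strictly above 150. Section 3.7.1 reports rises of more than 20% over two weeks after dose reductions without interruption. A 20% rise gives 100 × 1.20 = 120, or 125 × 1.20 = 150. That figure is a lower bound from other trials and a different setting, so it illustrates and does not predict.

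**Size for one patient.** 1/20 = 5 percentage points of the discontinuation proportion. It is also 5 points of the response proportion if that patient's responder status changes.

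**The case against.** The best counter-argument is that the rules act in sequence. A patient restarted on Day 7 at 120 who exceeds 150 by Day 21 satisfies both the re-challenge and the stopping rule. Sections 6.4 and 8.2.1 describe platelet rebound after cessation and rapid recovery that overshoots baseline, so many patients may cross 150 in time. Entry requires platelets of at least 250, dose reduction starts below 150, and Section 3.7.1 reports no patient in the essential thrombocythemia study below 75 by Day 28. Holds may therefore be uncommon, although that evidence covers another disease and an early period. Re-challenge is conditional on safety, the current dose may be maintained, and the Medical Monitor can be consulted.

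Most of this stands, and it rules out several stronger readings that a reader might infer:

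- *Every patient recovering through 100 to 150 is restarted, reduced and discontinued.* The stopping rule takes effect only at the end of its window, and a patient who passes 150 in time is not stopped.
- *A restarted patient is on course for discontinuation.* The rebound statements do not support that as the expected outcome.
- *The dose must be cut twice at the restart visit (for example 40 × 0.5 = 20, then 20 − 10 = 10 mg/d).* The reapply footnote can equally be read as governing later counts, and discretion to maintain the dose covers that row.
- *Any discontinued patient becomes a nonresponder.* Section 12.5 names patients without a response by Week 36 or who drop from the trial. Stopping drug leads to follow-up visits, and nothing says that an already sustained response is lost.

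The discretion does not reach the platelet item in Section 8.2.3, which is mandatory. A site may well treat it as overriding Table 1, but the protocol does not say so, and it does not say when the 21 days start.

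**Conclusion.** The inconsistency is real and is in the current dosing text. It has four parts: unlinked recovery thresholds of 100 and 150; no start for the 21-day clock; no precedence between Table 1 and Section 8.2.3; and a mismatch at exactly 150. The direct clash between restarting and discontinuing assumes that the clock starts with the hold and that the count is 100 to 150 at Day 21 without having exceeded 150. The overlap with the down-titration row can arise earlier but is softened by discretion.

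The number of patients affected cannot be computed, because the documents give no rate of holds for platelets below 50. For each affected patient the discontinuation proportion can move by 5 points of 20. The response proportion can move by the same amount only if discontinuation comes before a sustained 12-week response. Correction is warranted despite the unknown frequency, because instructions conflict in the toxicity that the protocol ranks as its main risk.

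**What to change.** Reconcile Table 1 and its footnotes (Section 7.2.2 and the synopsis), Section 7.2.2.3, Section 8.2.3 and the synopsis stopping rules. The revised text should:

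1. use one consistent set of platelet thresholds, with matching treatment of boundary values, for hold, re-challenge, the first titration after re-challenge, and discontinuation;
2. state the event that starts the 21-day clock and which count decides the test;
3. state which rule prevails when more than one applies;
4. give the required level in Section 7.2.2.3 as a number or a cross-reference.

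The sponsor's clinical team and the SAB should choose the values; none is proposed here. Any discontinuation already made under the conflicting text should be flagged in the safety listing.

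The cost is a wording amendment and a clarification to sites. Weekly counts are already required during a hold. After a restart the scheduled visits are monthly from Week 16, so if the chosen clock can run past the restart, the amendment should check that a count falls inside the window.

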9 STUDY VISIT PROCEDURES

This section provides comprehensive detail on the visits and assessments required; this section should serve as the main guidance for use during study visits. The Schedule of Assessments (Appendix 16.1) contains these details in schematic form and is provided for use in a supportive/reference capacity only. In an effort to maintain clarity while facilitating a modicum of brevity, the 'Terms' in Table 2 will be utilized to encompass the broader 'Protocol Meaning' as stated.

Note: If at any time additional clinical evaluation outside of the visit schedule is deemed necessary by the Investigator, then unscheduled visits should occur as appropriate.

Table 2: List of Protocol Terms and Meanings

Term	Protocol Meaning
Adverse Events and Concomitant Medications	Use non-directive questions (i.e. , "How are you feeling") to query patient re: any AEs that may have occurred. Also, inquire about medication changes since the last visit.
Limited Physical Examination, including Vital Signs	
 • Weight • Review of body systems for changes from previous visit • Vital signs, after patient has sat semi-supine for ~3 minutes, of: 
 ○ Heart rate ○ Respiratory rate ○ Temperature ○ Systolic/diastolic blood pressure • Spleen measurement – The spleen edge is determined by palpation, measured in centimeters, using a soft ruler/tape, from the costal margin to the point of greatest splenic protrusion in the mid-clavicular line. The spleen should be measured in the same manner at all visits.
MFSAF	
MFSAF is to be completed in the patient's native language during Screening (as close to Day -7 as possible), and within the 2 days leading up to or on the day of every visit throughout the study except for any additional bi-weekly visits implemented after Week 12 for patients whose dose has not stabilized. Ideally, the MFSAF will be completed at the same time and day each week for consistency. Date of completion should be documented each time the MFSAF is completed.
 
Please refer to the Study Reference Manual for additional instructions.

Term	Protocol Meaning
Bone Marrow Sampling	
 Aspirate (sample taken from first pull, whenever possible, and no later than the second) and biopsy collected as per site standard procedure. During Screening, UNLESS performed within the 3 months prior to the first dose of bomedemstat AND bone marrow biopsy slides or the formalin fixed paraffin embedded block are available from that sampling and can be provided to the central laboratory for review. Local laboratory generated fibrosis scores will be used at Screening to ensure eligibility. See Appendix 16.3 for fibrosis grading. A central pathology laboratory will perform morphology and fibrosis grading and store samples for correlative studies (Section 10.1.2). Note: Results available from site routine work-up such as morphology, cytogenetics, other genetic interrogations will be collected for study purposes either via the eCRF or through collection of local reports.
Dosing Instructions	
 Instruct patients to refer to their Dosing Card every day for details on bomedemstat dosing and what to do if a dose is missed Take their bomedemstat in accordance with Section 7.2.2 Handle any missed bomedemstat doses as per Section 7.2.2.2 Bring all medication to every clinic visit, including empty bottles
Administer bomedemstat	Administer bomedemstat with a glass of water and record exact time of dosing.
AE, adverse event; eCRF, electronic case report form; MFSAF, Myelofibrosis Symptom Assessment Form.	

9.1 Informed Consent

Patients must provide documented informed consent before undergoing any study-related procedures. The PI, or designee, will explain to the patient the aims of the study, the risks and benefits involved and that their participation is voluntary. Each patient will acknowledge receipt of this information and that they wish to participate in the study by giving written informed consent for their involvement in the study in the presence of the PI, or designee, who will also sign and date the Participant Information Sheet/Consent Form (PISCF). Time, date, name of the person taking consent and any questions raised by the patient must be documented in the source data.

9.2 Screening Period, Including Enrollment

The below assessments may be performed on the same day or multiple days, as needed, throughout the 28-day Screening period. If the patient screen fails at any time during the Screening period, document the reason(s) in the source data and on the Screening & Enrollment log.

9.2.1 Screening (Days -28 to Day -1)

- Review and confirm that patient meets all Inclusion and no Exclusion Criteria
- Complete medical/medication history including:
 - Demographics
 - Confirmation of diagnosis *per* 2016 WHO criteria for PV (Appendix 16.2)
 - PV disease history (*i.e.*, past bleeding episodes and thromboembolic events)
 - Treatment history for: PV, including clinical course with hydroxyurea and/or other PV therapy; and, any previous malignancy, including chemotherapy, surgery and radiation
 - Phlebotomy history
 - All concomitant medication, in addition to any used in the 15 days prior to Screening
- Assess ECOG Performance Status (Appendix 16.4)
- Full physical examination (PE) – review of all body systems including vitals, height (without shoes), weight and spleen palpation
- MFSAF, to be completed as close to Day -7 as possible (See Study Reference Manual [SRM] for details)
- Hematology with auto or manual differential (as needed to ensure all analytes are resulted)
- Serum chemistry, including erythropoietin (if test is available at institution)
- Coagulation (PT/aPTT/INR)
- Serum pregnancy test for POCBP
- Urinalysis
- Germline sample(s) for Central Laboratory genomic analysis
- Bone marrow aspirate and biopsy for morphology review and correlative research UNLESS performed within the 3 months prior to the first dose of bomedemstat **AND** bone marrow biopsy slides or the formalin fixed paraffin embedded block are available from that sampling and can be provided to the central laboratory for review. **Importantly**, fibrosis scores will be performed locally on Screening samples to enable assessment of patient eligibility.
- Instruct patient regarding washout to ensure prior therapy for condition under study is discontinued for 2 weeks (4 weeks for interferon) prior to study drug initiation. Phlebotomy may continue as clinically indicated.
- Schedule next clinic visit

9.2.2 Enrollment

For eligibility purposes, the following should be reviewed and/or confirmed:

- History of recent surgical procedures

- Recent use of investigational drugs
- Laboratory results will be assessed by the PI before enrollment. Any laboratory values confirmed on re-examination to be clinically significant by the PI and that would jeopardize the safety of the patient or impact on the validity of the study results will result in exclusion of that patient.

Once Screening procedures have been performed and it is confirmed that the patient can be enrolled, patients will be enrolled in accordance with procedures detailed in the SRM.

9.2.3 Last Day of Screening Period (Day -1)

- On Day -1, contact the patient and remind them to:
 - Report to the clinic the following day at the agreed time
 - Fast overnight (at least 8 hours) for PK purposes

9.3 Initial Period of Treatment (36-Weeks)

Procedures are presented below for each visit by assessments performed pre-dose, at dosing, and post-dose (as applicable).

9.3.1 Day 1 – Treatment Start

The below assessment has a visit window which permits conduct either pre- or post- Day 1 dose:

- Radiologic/Imaging assessment of spleen volume (± 2 day visit window)

9.3.1.1 Pre-Dose Day 1

- AEs and Concomitant Medications
- Assess ECOG Performance Status (Appendix 16.4)
- Limited PE, including vital signs, weight, and spleen palpation
- Ensure MFSAF is completed during visit if not completed earlier in the -2 day window (see SRM for details)
- Hematology (CBC) with auto or manual differential (as needed to ensure all analytes are resulted)
 - Confirm platelet count $\geq 250 \times 10^9/L$ and ANC $\geq 1.5 \times 10^9/L$, with CBC performed up to 2 days ahead of the C1D1 visit to avoid delays in dispensation due to pending lab results.
 - Establish baseline with a pre-dose blood sample collected on C1D1.
- Serum chemistry
- Coagulation (PT/aPTT/INR)
- Serum pregnancy test for POCBP

- Urinalysis
- Germline sample(s) for Central Laboratory genomic analysis, if not collected earlier in Screening
- PK sampling within 60 minutes prior to bomedemstat dosing
- Blood samples for Central Laboratory cytokine analysis
- Blood sample for Central Laboratory genomic analysis
- Blood sample for Central Laboratory correlative research
- Dispense doses sufficient until the next visit and provide Dosing Instructions
- Ensure patient continues to meet eligibility criteria prior to dosing

9.3.1.2 Dosing Day 1

- Administer bomedemstat and record the exact time of dosing in the patient's notes. Fasting should continue until 1 hour post-dose; water *ad libitum* is permitted during this time.

9.3.1.3 Post-Dose Day 1

Patients should remain in clinic for at least 2 hours post first dose and will need to undergo PK sampling through 6 hours post first dose

- PK sampling should occur at the following post-dose time-points with the exact time of sampling recorded in the patient's notes:
 - 1 hour (± 15 minutes)
 - 2 hours (± 30 minutes)
 - 4 hours (± 30 minutes)
 - 6 hours (± 60 minutes)
- Query for AEs, using non-directive questions (*i.e.*, "How are you feeling")
- Schedule next clinic visit

9.3.2 Bi-Weekly Visits - Weeks 2, 4, 6, 8, 10, 12 (± 2 days*)

*The ± 2 day visit window applies to the visit (*e.g.*, 'Week 2/Day 15' visit may be conducted on Day 13, 14, **15**, 16 or 17 as dictated by site and patient schedule), and not to individual assessments, unless otherwise noted. To clarify, the expectation is that all required assessments will be done on a single visit day with the exception of those specifically noted below.

- AEs and Concomitant Medications
- Assess ECOG Performance Status (Appendix 16.4)

- Limited PE, including vital signs, weight and spleen palpation
- Ensure MFSAF is completed during visit if not completed earlier in the -2 day window (see SRM for details)
- Pre-dose: Blood sample for hematology (CBC) with auto or manual differential (as needed to ensure all analytes are resultd) and titration assessment**. If patient requires a dose hold, CBCs should be monitored at least weekly for safety and to enable re-challenge as soon as platelet counts return to the required level, if safe to do so.
- Perform drug accountability and collect study medication
- Dispense doses sufficient until the next visit and provide Dosing Instructions
- Schedule next clinic visit

****Important:** may be performed up to 2 days ahead of the main visit to avoid delays in dispensation due to either pending lab results or pharmacy procedures and to facilitate all laboratory sampling occurring the same day as the hematology sampling needed for the titration assessment. For example, if a visit is scheduled on a Wednesday, these assessments may be performed Monday or Tuesday, to ensure bomedemstat is dispensed and available for collection at the Wednesday visit.

9.3.2.1 Week 2 (Day 15) and Again at Either Week 4 (Day 29), Week 6 (Day 43) or Week 8 (Day 57) Only

- On the day prior to the applicable study visits, the study coordinator (or site representative) will contact the patient and:
 - Collect and record the exact time the patient took their bomedemstat that day
 - Remind patient that an overnight fast (at least 8 hours) is required for PK purposes and dosing of bomedemstat will occur in the clinic the following day as PK sampling is required

